Appendix 5: Modified Hachinski ischemic scale (m-HIS) (95)

	Feature	Yes	No
H1	Abrupt onset	□2	□0
H2	Stepwise deterioration	□1	□0
НЗ	Somatic complaint	□1	□0
H4	Emotional incontinence	□1	□0
Н5	History or presence of hypertension	□1	□0
Н6	History of strokes	□2	□0
H7	Focal neurological symptoms	□2	□0
Н8	Focal neurological signs	□2	□0
Н9	Total (attention : score ≥4 can be chosen)		

Appendix 6: World Health Organization University of California-Los Angeles, Auditory Verbal Learning Test (WHO-UCLA AVLT (84)

On each of 3 learning trials, 15 unrelated words (all nouns) are presented orally at the rate of one word per second and immediate free recall of the words is elicited. The number of correctly recalled words on each trial is recorded. Following a 30-minute delay filled with unrelated testing, free recall of the original 15 word list is elicited. In cued recall, the experimenter prompts the subjects with the word category. Finally, a yes/no recognition test is administered which consists of the original 15 words and 15 randomly interspersed distracter words. The number of target "hits" and false positive responses are recorded.

	Text 1	Text 2	Text 3		Delay reca
arm				arm	
cat				cat	
axe				axe	
bed				bed	
airplane				airplane	
ear				ear	
dog				dog	
hammer				hammer	
chair				chair	
car				car	
eyes				eyes	
horse				horse	
knife				knife	
clock				clock	
bicycle				bicycle	
Item categ	ory	Record			
a body par		arm		ear	eyes

Item category	Record		
a body part	arm	ear	eyes
animal	at cat	dog	horse
tools	axe	hammer	knife
furniture	□ bed	Chair	clock
vehicle	airplane	car	bicycle

	Yes	No		Yes	No
mirror			mouse		
hammer			tree		

[figure not shown]
knife		arm	
candle		nose	
motorbike		sun	
axe		truck	
clock		eyes	
chair		fish	
airplane		ear	
tortoise		bicycle	
horse		snake	
thigh		bench	
dog		bus	
table		bed	
cat		car	

Appendix 7: Trail making test (TMT) (86)

Part A

[figure not shown]
Practice test

Administration: The following are some circles with numbers in the circle. I would like to ask you to connect in the order of 1-2-3... with a pen. Note: Do not leave the pen tip away from the paper and the line drawn must pass through the graphic. If I am wrong, I will point out that you need to go back and paint again. Let us give it a try now. The sooner you paint, the better. Are you ready? Start! Note: The following is a practice test, not scored. Correct every time you make a mistake, and tell the correct connection method, while actively encouraging.

Actual test

Administration: There is a similar circle diagram here, please connect it again as above. Please note that the faster you draw, the better. Do not leave the pen tip and the lines drawn must pass through the graphic. Start here (pointing to the starting point) until here (pointing to the end). Ready? Start. (time)

[figure not shown]

[figure not shown]
- 7.1.1 All digital completion time (0-150) seconds (if 150 seconds is not completed, record 150)
- 7.1.2 Number of errors(0-25; 88=Not applicable)
- 7.1.3 Correct number_(0-25; 88=Not applicable)

Part B

Administration: The following are 1-13 white circle numbers and 1-12 black circle numbers. They are also scattered. Please connect them in order, i.e. white circle 1 - black circle 1 - white circle 2 - black circle 2... Note: Do not leave the pen tip away from the paper and the line drawn must pass through the graphic. If I am wrong, I will point out that you need to go back and paint again. Let us give it a try now. The sooner you paint, the better. Are you ready? Start!

Practice test

- 7.2.1 All digital completion time (0-300) seconds (if 300 seconds is not completed, record 300)
- 7.2.2 Number Sequence Error Number_(0-25; 88=Not applicable)
- 7.2.3 Correct number of lines_(0-24; 88=Not applicable)

Appendix 8: Digit span test (DST) (87)

This task consists of two parts. Digits forward is administered first and requires the repetition of digits in the same order presented, while in digits backwards participants must repeat digits in an inverse or backwards order. Text 2 is administered even if the participant fails in Text 1.

	Text 1		Text 2
3	5-8-2	3	6-9-4
4	6-4-3-9	4	7-2-8-6
5	4-2-7-3-1	5	7-5-8-3-6
6	6-1-9-4-7-3	6	3-9-2-4-8-7
7	5-9-1-7-4-2-8	7	4-1-7-9-3-8-6
8	5-8-1-9-2-6-4-7	8	3-8-2-9-5-1-7-4
9	2-7-5-8-6-2-5-8-4	9	7-1-3-9-4-2-5-6-8
10	5-2-7-4-9-1-3-7-4-6	10	4-7-2-5-9-1-6-2-5-3
			Digit span

	Text 1		Text 2
2	2-4	2	5-8
3	6-2-9	3	4-1-5
4	3-2-7-9	4	4-9-6-8
5	1-5-2-8-6	5	6-1-8-4-3
6	5-3-9-4-1-8	6	7-2-4-8-5-6
7	8-1-2-9-3-6-5	7	4-7-3-9-1-2-8
8	9-4-3-7-6-2-5-8	8	7-2-8-1-9-6-5-3
			Backwards digit span

Appendix 9: Boston naming test (BNT) (88)

Administration: "I will show you some pictures now, please tell me what these pictures are."

If the tester fails to answer the answer, he is prompted: For example, "This is (plant), is there another name?"

If you still can't answer, then three answers are given in order to let the tester choose. Remember to record every answer of the testier, whether correct or not (only calculate the score of spontaneous naming: correct = 1, answer = 0).

	Picture	Answer	If wrong,	If the answer	Answer	If wrong,	If the prompt sti	ill answers the	error, please
	1100010		specific		(yes = 1;	specific	select (circle the		
			record	prompt	wrong = 0)	record	(******)
		0)		r · r·					
9.1	2. Tree			plant			Peach blossom	Tree	Fireworks
9.2	3. Pen			Used for			straw	Original ball	pen
				writing				pen	
9.3	6. Scissors			tool			Scissors	clamp	Spoon
9.4	8. Flowers			plant			Vegetables	straw hat	flower
9.5	9. Saw			Woodworkin			Machine gun	Saw	Knife
0.6	10. 5			g equipment			3.6	*** ***	D
9.6	12. Broom			Used for			Mop		Broom
0.7	*14 N.C. 1			cleaning			M. 1	brush Cauliflower	111
9.7 9.8	*14. Mushroom			food Inside the			Mushroom		umbrella
9.8	15. Hangers			wardrobe			roof	hanger	hook
9.9	16. Wheelchair			Patient use			Executive	trolley	wheelchair
9.9	10. Wheelchan			ratient use			chair	Honey	Wilecichan
9.10	17. Camel			animal			camel	mountain	Cattle
9.11	21 racquet			Sporting			Ping pong	racquet	mirror
	•			goods			paddle	_	
9.12	22. Snail			animal			snails	Squid	scallop
9.13	24. Seahorse			Marine life			hook	abalone	Seahorse
9.14	25. Darts			Used to			Target	Darts	rocket
				throw					
9.15	30. Harmonica			Musical			Harmonica	Air	box
0.4.5	24 71 1			instrument			G 11 10	conditioner	
9.16	31. Rhinoceros			animal			Canned knife	hippo	rhinoceros
9.17	33. Igloo			Used to live			Ice house	Grass house	grave
9.18	36. Cactus			plant			Iron tree	cactus	cross
9.19	37 escalator			Use up and down			Sliced bread	Slide	escalator
9.20	38. Harp			Musical			harp	floor lamp	piano
				instrument					
9.21	42. Stethoscope	;		Doctor			Earphone	Stethoscope	sphygmomano meter
9.22	43. Pyramid			In Egypt			Zongzi	Sphinx	pyramid
9.23	46. Funnel			Pour water			Funnel	Ice cream cones	Pump
9.24	47. Accordion			Musical			Harmonica	accordion	Blinds
ノ.ムマ	17. Accordion			instrument			Harmonica	accordion	Dillius
9.25	50. Compass			painting			Cotton pliers	ruler	Compasses
9.26	52. Tripod	†	†	For			tripod		easel
				photography			· -1r	arm	
9.27	54. tongs			Appliance			Spatula	tongs	canoe
9.28	57. Flower			Park has			Flower shed/	trash can	network
	shed/ trellis						trellis		
9.29	59. Protractor			stationery			Pound scale	Triangle ruler	Protractor
9.30	60. Abacus			Counting			Calculator	Abacus	Curtain
Total	9.31			9.32			9.33		

Appendix 10: Activities of daily living (ADL) (93)

Ask the insider to rate the following functions of the patient based on the information provided (assessed according to the level of intelligence).

Rating	Instrumental Daily Living Ability Scale (LADH) Scoring Project
1	Ability to use the phone
	\square_1 , take the initiative to operate the phone - check the number, dial, etc.
	\square_2 , can dial a few familiar numbers
	\square_3 , can answer the phone but not dial the phone
	\Box_4 , cannot use the telephone
2	Shopping
	\square_1 , independently handle all shopping needs
	\square_2 , a small amount of shopping independently
	\square_3 , need to accompany on any purchase
	4, completely unable to shopping
3	Cooking
	\Box 1、 independently plan, prepare and make the right amount of meal
	\square_2 , if the raw materials can be prepared to prepare enough meal
	\square_3 , heating, serving or cooking, or cooking but not keeping the right amount
	\Box_4 . Need to prepare the meal and do it well
4	Hosting housework
	1, independently host housework or occasionally need help (such as heavy work needs family help)
	\Box_2 , do daily light physical housework such as washing dishes, making beds
	3, do daily light physical housework but cannot maintain an acceptable level of cleanliness
	_
	4, all housework needs help
	5, do not participate in any housework
5	Washing

	1, can complete a personal bath
	— 1, can complete a personal bath
	\square_2 , wash small pieces of clothing - wash socks, etc.
	\square_3 , all washing must be done by others
6	Transportation
	1, independent public transport or driving a car
	\square_2 , travel by taxi, but no bus
	\square_3 , take the bus when accompanied by others
	\Box_4 , can only travel by taxi or car with the help of others
	□5, no travel at all
7	Responsibility for the medical care
	\Box_1 , can take medicine seriously according to the correct time and dose
	\square_2 , if you prepare for each dose, you can take medicine
	\square_3 , you can't prepare your own medicine
8	Financial ability
	1, independently handle finance (budget, write checks, pay rent, bills, go to the bank), collect and maintain income channels
	\Box_2 , manage daily shopping, but need help in banking affairs and big shopping, etc.
	☐3、can't handle finance
ADL total scor	e

9 I*A*

Rating	Somatic Self-care Ability Scale (PSUS) Scoring Project
10	Bowel and bladder function at the toilet,
	\Box_1 , in the bathroom can be completely self-care, no incontinence
	\Box_2 , need to be reminded of self-cleaning, or need help, or a small number of accidents (at
	least once a week)
	☐3、dirty or wet during sleep, more than once a week
	\Box_4 , dirty or wet when awake, more than once a week
	□ ₅ , incontinence

11	Eating
	1, no need to help when eating
	\Box_2 , eating a small amount of time to eat and/or need to prepare special food, or need help after cleaning after meals
	\Box_3 , need moderate help for meal, and it is not neat
	\square_4 , all meals need a lot of help
	5, can't eat at all, and resist feeding by others
12	Dressing
	\Box_1 , wear clothes, undress, and choose clothes from your wardrobe
	\square_2 , wearing clothes and undressing, need a small amount of help
	\square_3 , need moderate help in dressing and choosing clothes
	\Box_4 , need more help in wearing clothes, but with the help of others
12	5, can't wear clothes at all, and it is against the help of others
13	Carding (tidy, hair, nails, hands, face, clothes)
	1, always dressed neatly, properly decorated, no need to help
	\Box_2 , can properly decorate themselves, occasionally need a small amount of help, such as repairing beard
	\square_3 , need moderate or reasonable help or guidance in combing
	4, all combing matters need help, but can be kept neat after others help
1.4	\Box_5 , actively oppose the efforts of others to help sort out
14	Walking
	\square_1 , walk to the venue or urban area
	\square_2 . Walk in the residential area or walk near a street
	3, walking needs help (choose 1) a() cane, b() walker, c() wheelchair
	☐ 1-In and out without help

	\Box_2 -In and out need help
	\Box 4、don't need to sit in a chair or a wheelchair, but you can't push it yourself without
	help
	\square_5 , more than half of the time bedridden
15	Bathing
	\Box_1 , take a bath (bath, shower, bath), no need to help
	\square_2 , need help when getting in and out of the tub
	\square_3 , only wash your face and hands, cannot wash other parts of the body
	\Box_4 , cannot take a bath, but with others to bathe him
	\Box 5. cannot take a bath, and resist efforts to keep him clean

16 BADL total score

17 ADL total score (IADL+BADL)

The total score below 16 is completely normal, and greater than 16 points have different degrees of functional decline, up to 64 points. The single item is divided into 1 normal, 2 to 4 is divided into functional decline, where there are 2 or more than \geq 3 points, or the total score is \geq 22 points, there are obvious obstacles to function

Appendix 11: Clinical Dementia Rating (CDR) (83)

This is a semi-structured interview. Please ask all of these questions. Ask any additional questions necessary to determine the subject's CDR. Please note information from the additional questions.

Memory	Onestions	for	Informant:
MEHIOIA	Questions	101	minui mami.

1.	Does he/she have a problem with his/her memory or thinking? 1a. If		Yes	No	
	yes, is this a consistent problem (as opposed to inconsistent)?		Yes	No	
2.	Can he/she recall recent events?	Usually	Somet	imes	Rarely
3.	Can he/she remember a short list of items (shopping)?	Usually	Somet	imes	Rarely
4.	Has there been some decline in memory during the past year?		Yes	No	
5.	Is his/her memory impaired to such a degree that it would have				
	interfered with his/her activities of daily life a few years ago (or pre-retirement activities)? (collateral sources opinion)		Yes	No	
6.	Does he/she completely forget a major event (e.g., trip, party, family wedding) within a few weeks of the event?	Usually	Somet	imes	Rarely
7.	Does he/she forget pertinent details of the major event?	Usually	Somet	imes	Rarely
8.	Does he/she completely forget important information of the distant past (e.g., birthdate, wedding date, place of employment)?				
		Usually	Somet	imes	Rarely
location there).	of the event, time of day, participants, how long the event was, when it ended Within 1 week: Within 1 month:	and how the s	subject or of	her partic	pants got
10	When was he/she born?				
11.	Where was he/she born?				
12	What was the last school he/she attended? Name Place				-
13	Grade What was his/her main occupation/job (or spouse's job if subject was not e	mployed)?			
14	What was his/her last major job (or spouse's job if subject was not employed	ed)?			
15	When did he/she (or spouse) retire and why?				

Orientation Questions for Informant:

How often does he/she know of the exact:

1. Date of the Month?

	Usu	ıally	Sometimes	Rarely	Don't Know
2.	Month?				
	Usu	ıally	Sometimes	Rarely	Don't Know
3.	Year?				
	Usu	ially	Sometimes	Rarely	Don't Know
4.	Day of the	e Week?			
	Usu	ially	Sometimes	Rarely	Don't Know
5.	Does he/sl	he have diffici	ulty with time relations	ships (when event	s happened in relation to each other)?
	Usu	ıally	Sometimes	Rarely	Don't Know
6.	Can he/sh	e find his/her	way about familiar stre	eets?	
	Usu	ıally	Sometimes	Rarely	Don't Know
7.	How often	n does he/she l	know how to get from	one place to anoth	ner outside his/her neighborhood?
,.			_		-
	Usu	ıally	Sometimes	Rarely	Don't Know
8.	How often	can he/she fi	nd his/her way about in	ndoors?	
	Usu	ıally	Sometimes	Rarely	Don't Know
Jud	gment and	Problem Sol	ving Questions for In	formant:	
1.	In general,	if you had to	rate his/her abilities to	solve problems at	the present time, would you consider them: As good as
	the	ey have ever b	een		
	Go	ood, but not as	good as before		
	Fa	ir			
	Po	or			
	No	ability at all			
2.	Rate his/he	er ability to co	pe with small sums of	money (e.g., mak	e change, leave a small tip):
	No	loss			
	Son	me loss			
	Sev	vere loss			
3.	Rate his/he	er ability to ha	ndle complicated finan	icial or business tr	ansactions (e.g., balance check-book, pay bills):
	No	loss			

	Severe loss					
	4. Can he/she handle a household	emergency (e.g., pl	umbing leak, sma	ll fire)?		
	As well as before					
	Worse than before beca	use of trouble think	ing			
	Worse than before, ano	ther reason (why)				
	5. Can he/she understand situation	ns or explanations?				
	Usually	Sometimes	Rarely	Don't Know		
	6. Does he/she behave* appropria with other people?	ately [i.e., in his/her	usual (premorbid)	manner] in social situation	ons and int	eractions
	Usually	Sometimes	Rarely	Don't Know		
	*This item rates behavior, not appe	arance.				
	Community Affairs Questions for	r Informant:				
	Occupational					
1.	Is the subject still working? If not applicable, proceed to item yes, proceed to item 3 If no, proceed to item 2	4 If		Yes	No	N/A
2.	Did memory or thinking problems to retire? (Question 4 is next)	contribute to the su	abject's decision	Yes	No	D/K
3.	Does the subject have significant or thinking?	difficulty in his/her	job because of pro	blems with memory		
	,	Sometimes	Usually	Don't Know		
	Social					
4.	Did he/she ever drive a car?				Yes	No
5.	Does the subject drive a car now?				Yes	No
6.	If no, is this because of memory of	or thinking problems	3?		Yes	No
7.	If he/she is still driving, are there I	problems or risks be	cause of poor thin	king?	Yes	No
*8.	Is he/she able to independently sh	op for needs?				
	Rarely or Never (Needs to be accompand on any shopping trip)	Sometimes ied (Shops for lin of items; buys du or forgets needed	plicate items	Don't Know		
9.	Is he/she able to independently carr	ry out activities outs	side the home?			
	Rarely or Never (Generally unable perform activities	Sometimes (Limited and/or routing, e.g.,	Usually (Meaningful participation	Don't Know		

Some loss

participation in activities, or meetings; trips to voting) without help)

or meetings, ar	Ρ
beauty parlor)	•

10. Is he/she taken to social functions outside a family home? If no, why not?		Yes	No
11. Would a casual observer of the subject's behavior think the sub	ject was ill?	Yes	No
12. If in nursing home, does he/she participate well in social functi	ons (thinking)?	Yes	No
*Is there enough information available to rate the subject's level of i If not, please probe further.	impairment in community af	fairs? Yes	No
Community Affairs: Such as going to church, visiting with friends such as bar association, other professional groups, social clubs, serv			organizations
*Please add notes if needed to clarify subject's level of functioning	in this area:		
Home and Hobbies Questions for Informant:			
1a. What changes have occurred in his/her abilities to perform	n household chores?		
1b. What can he/she still do well?			
2a. What changes have occurred in his/her abilities to perform	n hobbies?		
2b. What can he/she still do well?			
3. If in nursing home, what can he/she no longer do well (H a	and H)?		
Everyday Activities (Blessed):	No loss	Severe loss	
4. Ability to perform household tasks	0 0.5	1	
Please describe:			
5. Is he/she able to perform household chores at the level of: one. Informant does not need to be asked directly).	(Pick		
No meaningful function. (Performs simple activities, such as making a bed, only	ly with much supervision)		
Functions in limited activities only . (With some supervision, washes dishes with acceptab	le cleanliness; sets table)		
Functions independently in some activities . (Operates appliances, such as a vacuum cleaner; prepare	ares simple meals)		
Functions in usual activities but not at usual level.			

Normal function in usual activities.

IMPORTANT:

Is there enough information available to rate the subject's level of impairment in HOME & HOBBIES?

If not, please probe further.

Homemaking Tasks: Such as cooking, laundry, cleaning, grocery shopping, taking out garbage, yard work, simple care maintenance, and basic home repair.

Hobbies: Sewing, painting, handicrafts, reading, entertaining, photography, gardening, going to theater or symphony, woodworking, participation in sports.

Personal Care Questions for Informant:

*What is your estimate of his/her mental ability in the following areas:

A.Dressing(Blessed)	Unaided	Occasionally misplaced buttons, etc.	Wrong sequence commonly forgotten items	Unable todress
	0	1	2	3
B.Washing,grooming	Unaided	Needs Prompting	Sometimes needs help	Always or nearly always needs
	0	1	2	3
C.Eating habits	Cleanly proper utensils	Messily; spoon	Simple solids	Has to be fed completely
	0	1	2	3
D.Sphincter control (Blessed)	Normal complete control	Occasionally wets bed	Frequently wets bed	Doubly incontinent
,	0	1	2	3

*

A box-score of 1 can be considered if the subject's personal care is impaired from a previous level, even if they do not receive prompting.

Memory Questions for Subject:

1. Do you have problems with memory or thinking?

A few moments ago you me something about tho day, participants, how lo participants got there).	se? (Prompt for				
	Within 1 week	ζ.			
.0 – Largely correct	_				
	0.5				
.0 – Largely incorrect					
	Within 1 mon	th			
.0 – Largely correct	_				
	0.5				
.0 – Largely incorrect					
I will give you a name a after me: (Repeat until the Elements	he phrase is corre	ectly repeated or to a r	naximum of three	trials).	5
	he phrase is corre 1 John John John	2 Brown, Brown, Brown,	_		5 Chicago Chicago Chicago
after me: (Repeat until ti	he phrase is corre 1 John John John	2 Brown, Brown, Brown,	naximum of three 3 42 42	trials). 4 Market Street, Market Street,	Chicago Chicago
after me: (Repeat until ti Elements (Underline elements rep	he phrase is corre 1 John John John	2 Brown, Brown, Brown,	naximum of three 3 42 42	trials). 4 Market Street, Market Street,	Chicago Chicago
after me: (Repeat until till Elements (Underline elements rep When were you born?	he phrase is corre 1 John John John eated correctly in -	2 Brown, Brown, Brown,	3 42 42 42 42	trials). 4 Market Street, Market Street,	Chicago Chicago
after me: (Repeat until ti Elements (Underline elements rep When were you born? Where were you born? What was the last school Name	he phrase is corre 1 John John John eated correctly in -	2 Brown, Brown, Brown,	naximum of three 3 42 42	trials). 4 Market Street, Market Street,	Chicago Chicago
after me: (Repeat until ti Elements (Underline elements rep When were you born? Where were you born? What was the last school Name	he phrase is corre 1 John John John eated correctly in 1 you attended?	Brown, Brown, Brown, each trial).	naximum of three 3 42 42 42 42 42	trials). 4 Market Street, Market Street,	Chicago Chicago

Yes No

Elements	John	Brown,	3 42	Market Street,	5 Chicago
rientation Questions fo	or Subject:				
decord the subject's answ	ver verbatim for e	each question			
. What is the date today	?			Correct Incorrect	
. What day of the week	is it?			Correct Incorrect	
. What is the month?				Correct Incorrect	
. What is the year?				Correct	
				Incorrect	
. What is the name of th	nis place?			Correct Incorrect	

Incorrect

7.	What time	is it?	Correct Incorrect
8.	Does the su	abject know who the informant is (in your judgment)?	Correct Incorrect
Juo	lgment and	Problem Solving Questions for Subject:	
		s: If initial response by subject does not merit a grade 0, press the matter est understanding of the problem. Circle nearest response.	to identify the
Sin	nilarities:		
	Example:	"How are a pencil and pen alike? (writing	
		instruments) How are these things alike?"	
	Subject's R	desponse	
		1. turnipcauliflower	
		(0 = vegetables)	
		(1 = edible foods, living things, can be cooked,etc.)	
		(2 = answers not pertinent; differences; buy	
them)			
		2. deskbookcase	
		(0 = furniture, office furniture; both hold books)	
		(1 = wooden, legs) (2 = not pertinent, differences)	
Dif	ferences:		
	Example: "	What is the difference between sugar and vinegar?	
	(sweet vs s	our) What is the difference between these things?"	
		3. liemistake	

(0 = one deliberate, one unintentional)

(1 = one bad the other good - or explains only one)

(2 = anything else, similarities)

4. river.....canal

(0 = natural - artificial)

(2 = anything else)

Calculations:

5. How many nickels in a dollar?

Correct In

Incorrect

6.How many quarters in \$6.75?

Correct

Incorrect

7.Subtract 3 from 20 and keep subtracting 3 from

each new number all the way down.

Correct

Incorrect

Judgment:

8. Upon arriving in a strange city, how would you locate a friend that you wished to see?

(0 = try the telephone book, go to the courthouse for a directory; call a mutual

friend)

(1 = call the police, call operator (usually will not give address))

(2 = no clear response)

9. Subject's assessment of disability and station in life and understanding of why he/she is present at the examination (may have covered, but rate here):

Good Insight

Partial Insight

Little Insight

CDR global

Use all the information you get to make the most appropriate judgments. Evaluate the six functional areas respectively, fill in the scores in the corresponding "_", and note that only when the decline of ability is caused by cognitive impairment can the score be scored. If the severity of dysfunction is between two levels, in principle, it shall be evaluated as the severity level. Finally, based on the scores of six functional areas, the global CDR is summarized according to the following principles:

- 1. Memory (M) is the main item, the other 5 items are the secondary items;
- 2. When M=0.5, CDR \neq 0, only =0.5or 1;
- 3. CDR=M (memory score):

- 1) When at least 3 secondary items are the same as the memory score;
- 2) When only 1 or 2 minor item scores = M, no more than 2 minor item scores are on either side of M;
- 3) When the scores of 3 secondary items are on one side of the memory score and the scores of the other 2 secondary items are on the other side of the memory score;
- 4) When at least 3 minor items are all 0, if M = 0.5, CDR = 0.5;
- 5) Only when 1 minor item ≥ 0.5 , if M = 0, CDR = 0.
- 4. CDR≠M (memory score):
- 1) When 3 or more minor item scores are greater than or less than M, CDR = most minor item scores;
- 2) When M = 0.5 and at least 3 minor items score ≥ 1 , CDR = 1;
- 3) When M = 0, 2 or more minor items ≥ 0.5 , CDR = 0.5;
- 4) When $M \ge 1$, CDR $\ne 0$, at this time, if most of the other minor items = 0, CDR=0.5.
- 5. Principle of near association: when the above principle is not met, CDR = M score of the closest secondary item (e.g., M and a secondary item score =3, 2 secondary item score =2, 2 secondary item score =1, CDR=2).

CDR (sum of boxes)

It refers to the sum of the scores of all six functional areas.

CDR (supplementary part)

The assessment shall be made according to the test conditions and shall not be included in the total score.

CLINICAL DEMENTIA RATING (CDR)

CLINICAL DEMENTIA RATING (CDR):	0	0.5	1	2	3
KATING (CDK):					

	Impairment				
	None 0	Questionable 0.5	Mild 1	Moderate 2	Severe
11.1 Memory	No memory loss or slight inconsistent forgetfulness	Consistent slight forgetfulness; Partial recollection of events; "benign" forgetfulnes s	Moderate memory loss; more marked for recent events; defect interferes with everyday activities	Severe memory loss; only highly learned material retained; new material rapidly lost	Severe memory loss; only fragments remain
11.2 Orientation	Fully oriented	Fully oriented except for slight difficulty with time relationshi ps	y with time relati	Severe difficulty with time relation ships; usually diso riented to time, of ten to place	Oriented to perso n only
11.3 Judgment ⪻ oblem Solving	Solves everyday pro blems & handles busines s & financial affai rs well; judgment good in re lation to past performance	Slight impairment in solving problems, si milarities, and differ ences	Moderate diff iculty in han dling proble ms, similariti es, and differ ences; social judgment usu ally maintain ed	Severely impaired in handling proble ms, similarities, an d differences; socia l judgment usually impaired	Unable to mak e judgments or solve problems
11.4 Community Af fairs	Independent function at usual level in job, shopping, volunteer and social groups	Slight impairment in these activities	Unable to function independently at these activities all though may still be engaged in some; appears normal to casual inspection	No pretense of independence ide home Appears well enough to be taken to functions outside a family home	Appears too ill t

11.5 Home and Ho bbies	erests well maintaine	Life at home, hobbi es, and intellectual i nterests slightly impa ired	Mild but definite impairment of fun ction at home; m ore difficult chore s abandoned; mor e complicated ho bbies and interest s abandoned	Only simple chore s preserved; very restricted interests, poorly maintaine d	No significant fu nction in home
11.6 Personal Care	Fully	capable of self-care	Needs prompting	Requires assistance i n dressing, hygiene, keeping of personal effects	Requires much help with per sonal care; fre quent incontine nce

Appendix12: Participating unit and participant number

A total of 8 digits: the number of each unit (3) + the number of the participant (5), with a horizontal bar in the middle. For example, the number of eighth participant in Xuanwu Hospital is 001-00008. The number of each participating unit is shown in the table below.

NO.	Unit name	NO.	Unit name
		110.	Cint name
001	Xuanwu Hospital, Capital Medical University	035	Jiangxi Provincial People's Hospital
002	Beijing Tian Tan Hospital, Capital Medical University	.036	Anshanshi Changda the Hospital
003	Beijing Chao-Yang Hospital, Capital Medical University	037	Affiliated Zhongshan Hospital of Dalian University
004	Fu Xing Hospital, Capital Medical University	038	The First Hospital of China medical University

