3.2.4 Sample size

This study is planned to recruit 100 thousand subjects, from all participant centers that cover the North, South, East and Western parts of China.

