4.2 Neuropsychological assessment (See Appendix 1-11 for details)

Investigators should strictly follow the guidelines and scoring criteria, be consistent with different subjects and avoid inducing subjects. Patience is encouraged to complete the subject and, if needed, a short break. Check as far as possible in an independent, quiet space, try to be one-on-one with the subject to avoid outside interference.

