4.2.10 Activities of daily living (ADL) (93)

The ADL scale can evaluate the daily activities of the subject comprehensively, accurately and quickly. It consists of the physical life self-care scale and the instrumental ADL. There are 14 items, including two parts: first, the physical life self-care scale has a total of 6 items, including toilet, eating, dressing, grooming, walking and bathing; second, instrumental ADL has a total of 8 items, including call, shop, prepare meals, do housework, laundry, use transportation, take medicine and financing abilities. The higher the subject scores, the worse the ability of daily living.

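### ADL item 5 is a laundry item whose best level is bathing, so one person can score 1 or 3; separately, two CDR calculation items are printed in US coins

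*Protocol*

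**What the plan says.** **ADL.** Section 4.2.10 describes 14 items. Six are self-care items, bathing among them. Eight are instrumental, and that list includes "prepare meals, do housework, laundry, use transportation, take medicine and financing abilities". In Appendix 10 the corresponding item is item 5, headed Washing, with three levels:

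- Level 1 (best): "can complete a personal bath".
- Level 2: washes small garments such as socks.
- Level 3 (worst): other people do all the washing.

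Bathing is graded again, over five levels, as item 15. The note that closes Appendix 10 calls a total below 16 normal and a total above 16 some functional decline. It recognises marked impairment when two or more items score at least 3, or when the total is at least 22.

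Item 14, walking, has a level 4 stating that the person does not need a chair or wheelchair, and also that the person cannot push it without help.

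**CDR.** The calculation block in Appendix 11 has three items: "How many nickels in a dollar", "How many quarters in \$6.75" and a serial subtraction beginning "Subtract 3 from 20 and keep subtracting 3 from". Participants are recruited "from all participant centers that cover the North, South, East and Western parts of China". Section 4.2 says "Investigators should strictly follow the guidelines and scoring criteria" and refers to the appendices. Appendix 11 itself tells the interviewer to ask every question and to add others where needed.

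**The concern.** A graded item should run along one ability. Item 5 starts with bathing and moves to clothes, so its score depends on which line the rater treats as governing. No printed level describes doing all of one's own laundry, and loss of independent bathing could count in both item 5 and item 15.

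ADL appears in no entry criterion in section 3.2.1. It matters in two other places. Section 3.1 (item 5) plans to analyse change in daily-life ability over follow-up. Section 3.2.2(1) has participants who fail the MMSE or MoCA norms at follow-up complete all scales, after which the investigator decides on regrouping from the scores.

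The coin items raise a different question. Answering them needs the values of US coins as well as arithmetic, and no instruction says what to do when a participant lacks that knowledge. Raters at 68 centres could handle this differently. CDR = 0.5 is an MCI inclusion criterion, so variation in the Judgment box has a route to classification.

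**Working it through.** The plan gives no figure of its own on this point. The check applies the printed scoring rules.

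**ADL item 5**

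Inputs: 14 scored items with lowest level 1 (Appendix 10, items 1–8 and 10–15); item 5 levels 1 to 3; the cut-offs in the closing note of Appendix 10.

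1. All other items normal: total = 13 × 1 + item 5 = 14, 15 or 16. The ambiguity is worth at most 3 − 1 = 2 points. None of these totals exceeds 16 or reaches 22, and at most one item is at 3. Item 5 alone therefore crosses no decline cut-off. A total of exactly 16 falls between the below-16 and above-16 statements.
2. One other item at 3, the remaining 12 at 1:
   - item 5 scored 1: 3 + 12 + 1 = 16, with one item at 3 or more. Neither the decline nor the marked-impairment rule is met.
   - item 5 scored 3: 3 + 12 + 3 = 18, with two items at 3 or more. The total is above 16 and the two-item rule is met.

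In the second case the same person changes class according to which line of item 5 the rater reads.

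**CDR coin items**

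The expected answers are 1 / 0.05 = 20 and 6.75 / 0.25 = 27. Both need coin values; the serial subtraction does not.

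To see when a changed Judgment box alters global CDR, the other four secondary boxes were each set to 0, 0.5 or 1 (3⁴ = 81 profiles) and Judgment was raised by one level. Two rules in Appendix 11 were taken as deciding:

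- Memory 0: rule 4.3, "When M = 0, 2 or more minor items" at 0.5 or above, gives 0.5; otherwise 0.
- Memory 0.5: rule 4.2, three or more secondary boxes at 1 or above, gives 1; otherwise 0.5.

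| Memory | Judgment change | Profiles where global CDR changes | Condition |
|---|---|---|---|
| 0 | 0 to 0.5 | 8 of 81 | exactly one other box at 0.5 or more: 4 boxes × 2 levels |
| 0 | 0.5 to 1 | 0 of 81 | – |
| 0.5 | 0 to 0.5 | 0 of 81 | – |
| 0.5 | 0.5 to 1 | 24 of 81 | exactly two others at 1: 6 pairs × 2² settings of the rest |

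These are unweighted counts of profiles, not expected frequencies. Each one-level shift here adds 0.5 to the sum of boxes. The route that bears on MCI status is the last row: global CDR moves from 0.5 to 1, outside the MCI criterion.

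**The case against.** A reader might infer that both scales are mis-scored regardless of cognition and that both feed study entry. The documents do not support that.

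- **The Judgment box is not a count of correct answers.** Appendix 11 has the rater weigh all available information and score only decline caused by cognitive impairment. The domain also has similarities, differences, a judgment question, non-currency arithmetic and informant questions about money. Not knowing US coins is not cognitive decline under that rule. This stands and limits the effect, although nothing tells raters how to treat such a failure.
- **The memory-0 route does not alter MCI entry.** Section 3.2.1 also requires prominent memory loss. This stands.
- **A fixed rise of 0.5 to 1 point in the sum of boxes** has no source in the protocol.
- **Bias against rural or less educated people** is tempting to infer, since residence and education are among the factors studied. The protocol gives no data on familiarity with the coins. Community participants and normal controls have only MMSE and MoCA as their baseline cognitive assessment.
- **The fielded form is not shown.** Section 2.1 says most scales are translated or modified for Chinese use, and the bath wording may be a translation slip. Both remain possible. However, the appendix is the form to which section 4.2 refers, and it gives no other version.

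None of this removes the contradiction between section 4.2.10 and Appendix 10, item 5.

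**Conclusion.** The ADL defect holds as an internal contradiction with a scoring consequence: up to 2 points on the total, and a change of class where one other item is already at 3. It assumes that raters read level 3 as laundry, in line with section 4.2.10, while level 1 is taken as printed. Walking level 4 is self-contradictory as printed.

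The CDR point holds in a narrower form. Two of three calculation items are unsuited, as printed, to the population recruited. They add rater variation that can change global CDR only in borderline profiles, for example memory 0.5 with two other boxes at 1 or more and Judgment rated 1 instead of 0.5. How often such profiles occur cannot be derived from the protocol.

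Both points rest on the appended wording being what is administered. They do not show that scores already collected are wrong, and they do not justify re-rating past Judgment boxes. Those are global ratings and would need fresh clinical judgment in a cohort that began in 2008.

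**What to change.** 1. Reword Appendix 10 item 5 level 1 so that it describes doing one's own laundry, consistent with section 4.2.10 and with levels 2 and 3. Leave bathing to item 15.
2. Reconcile the two halves of walking level 4.
3. Replace CDR calculation items 5 and 6 with items of equal difficulty in local currency. If a localised form is already in use, append it in place of the printed one.
4. Record a form-version flag with each ADL and CDR assessment, so that longitudinal analyses can separate change in the participant from change in the form.

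The cost is a revision of form wording and a short note to raters. The downside is that earlier assessments need a version flag. With the study planned to run to 2038, most of the benefit falls on assessments still to come.
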